8.9 Safety Analysis

All safety analysis will be performed using the Full Analysis Set. No statistical comparisons will be performed.

8.9.1 Adverse Events

The latest Medical Dictionary for Regulatory Activities (MedDRA) will be used to code all AEs to a system organ class (SOC) and preferred term.

An AE (classified by preferred term) will be considered a treatment emergent adverse event (TEAE) if it occurred on or after the first dose in this study, and was not present prior to the first dose in this study, or it was present at the first dose in this study but increased in severity during the study.

Subject incidence of TEAEs will be tabulated by SOC and preferred term. Serious TEAEs, treatment-related TEAEs, grade 3/4 TEAEs, fatal TEAEs, TEAEs leading to study discontinuation, and TEAEs leading to treatment discontinuation will be summarized. Gastrointestinal TEAE will also be summarized.

Detailed listings for all AEs, SAEs, treatment related TEAEs, treatment related SAEs, AEs leading to the discontinuation, and death will also be generated. The severity will be based on Common Terminology Criteria for Adverse Events (CTCAE). If an AE cannot be graded based on CTCAE, the investigator will assign a severity based on 1 = mild, 2 = moderate, 3 = severe, 4 = life threatening, and 5 = Death related to AE.

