7.5.1 Visit Schedule

The Baseline Visit may occur in conjunction with the last scheduled visit from study UX007G-CL201. Assessments conducted at the last UX007G-CL201 visit will be used for Baseline data to avoid duplication. If the time elapsed between the last UX007G-CL201 study visit and the Baseline Visit for this study is > 1 month, the full panel of Baseline Visit assessments must be completed. Informed consent must be obtained prior to any Baseline procedures specific to the UX007G-CL202 study. Subjects will be provided UX007 treatment continuation only after all inclusion/exclusion criteria have been confirmed.

The Baseline Visit will be 2 days in duration to complete all assessments and the overnight EEG.

Subjects will return to the clinic at 3-month intervals from Baseline (\pm 1 week) during Year 1, and at 6-month intervals from Baseline (\pm 2 weeks) during Years 2 and 3 of the Treatment Extension Period to assess long-term safety and efficacy. Phone calls will take place 3-months between scheduled study site visits during Years 2 and 3 to collect adverse events and concomitant medications updates and to inquire about study drug consumption and remaining supply; in lieu of the phone call, subjects may visit the clinic at the study site's discretion. Additionally, optional study site visits may occur 3-months between scheduled study site visits during Years 2 and 3 to allow subjects to attain study drug as needed at the request of the Investigator. A Safety Follow-up Phone Call will be conducted 30-35 days after last dose of study drug. The last subject's Safety Follow-up Phone Call is the End of Study Time Point. The site personnel will initiate this safety follow-up telephone call to collect information on any ongoing or new AEs, SAEs, and concomitant medications. Appropriate follow-up should continue until all safety concerns, in the Investigator's opinion, are resolved. Minors who reach legal age during the course of the study must provide written informed consent when eligible. For subjects who discontinue prior to completing the study, every reasonable effort should be made to perform the Early Termination visit procedures within 4 weeks of discontinuation.

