7.5.4.1 Medical History and Triheptanoin Treatment History

Medical history will be obtained at the Baseline Visit for all subjects not previously enrolled in UX007G-CL201. General medical information includes subject demographics (date of birth, ethnicity, and sex) and a history of major medical illnesses, diagnoses, and surgeries. The review will also include an assessment of phenotypic characteristics associated with Glut1 DS, including seizures, cognitive impairment, movement disorders, and microcephaly. The specific history of Glut1 DS will be recorded, along with date of onset, clinical presentation, and date and method of confirmed diagnosis. Any available family history of Glut1 DS will be noted including diagnosis, disease course, treatment and outcome.

Glut1 DS maintenance treatment history, including UX007 (triheptanoin) treatment history, and relevant concomitant medications will be recorded (start date, stop date, dose, dose regimen). Treatments include prescribed diets, other standard of care treatments, and all other relevant concomitant medications (e.g. seizure medications, L-carnitine, vitamin supplements, etc.). Medications include prescription, over-the-counter, herbal and nutritional supplements. Any relevant concomitant therapy, including physical/occupational therapy will be recorded.

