7.6.3 Safety Analyses

The primary safety analysis will evaluate the incidence and frequency of AEs and SAEs, including clinically significant changes in safety parameters throughout the Treatment Extension Period. The incidence and frequency of AEs will be summarized by System Organ Class and Preferred Term, relationship to study drug, and severity. No formal hypothesis testing will be performed.

Safety will be evaluated by the incidence, frequency and severity of AEs and SAEs, including clinically significant changes from baseline to scheduled time points in:

- Vital signs and weight
- Physical examination
- Clinical laboratory evaluations
- Pregnancy testing
- Suicidal ideation and behavior assessments
- Concomitant medications

The analyses of safety will be performed on the safety analysis population.

All AEs will be coded using the Medical Dictionary for Regulatory Activities (MedDRA). The incidence and frequency of AEs will be summarized by System Organ Class (SOC), Preferred Term (PT), relationship to study drug, and severity. All reported AEs with onset

during treatment (i.e. treatment-emergent AEs) will be included in the analysis. For each AE, the percentage of subjects who experienced at least 1 occurrence of the given event will be summarized by treatment group. The numbers (frequency) and incidence rates of AEs and SAEs will be summarized during exposure to UX007 throughout the study. Special attention will be given to those subjects who died, discontinued treatment due to an AE, or experienced a SAE (e.g. summaries, listings, and narrative preparation, as appropriate).

Clinical laboratory data will be summarized by the type of laboratory test. The frequency and percentage of subjects who experience abnormal clinical laboratory results (i.e. outside of reference ranges) and/or clinically significant abnormalities after study drug administration will be presented for each clinical laboratory measurement.

Changes in findings from physical examinations will be tabulated and listed for each subject by examination category. If there are examination findings that change in more than one subject, these will be tabulated in a separate table and expressed as the number of subjects with the change out of the total.

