8.5.4 Adverse Event Reporting

8.5.4.1 General

All AEs (i.e. any new or worsening in severity or frequency of a preexisting condition) with onset after the subject signs consent for study participation must be promptly documented on the CRF. The Investigator is responsible for evaluating all AEs, obtaining supporting documents, and ensuring documentation of the event is adequate. Details of the AE must include severity, relationship to study drug, duration, and outcome.

All AEs will be collected from the time the subject signs informed consent through 30 days following the last dose of study drug. In addition, the Investigator should report any AE that occurs after this time period that is believed to have a reasonable possibility of being associated with study drug.

AEs ongoing at 30 days following the last dose of study drug should have a comment in the source document by the Investigator whether the event has recovered, recovered with sequelae, or stabilized.

8.5.5 Serious Adverse Events, Serious Adverse Drug Reactions, and Requirements for Immediate Reporting

Ultragenyx or its designee must be notified of any SAE that occurs at any time during the reporting period within 24 hours of the Investigator, designee, or site personnel's knowledge of the event. SAEs will be reported by completing and submitting SAE report forms to Ultragenyx or its designee.

Follow-up SAE information must be submitted in a timely manner as additional information becomes available. All SAEs regardless of relationship to study drug must be followed to resolution or stabilization if improvement is not expected.

All deaths, regardless of causality, occurring from the signing of the informed consent until 30 days following the last dose of study drug are to be reported as SAEs to Ultragenyx or its designee within 24 hours of knowledge.

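### SAP 8.9.1 defines treatment-emergent more narrowly than the protocol: read literally, recurrences of resolved terms and frequency-only worsening drop out of every TEAE table

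*SAP*

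**What the plan says.** **SAP 8.9.1** classifies by preferred term. An event on or after the first CL202 dose is a TEAE if the term "was not present prior to the first dose in this study, or it was present at the first dose in this study but increased", with severity as the only measure of increase. No last day is given. The incidence tables described there (overall, serious, treatment-related, grade 3/4, fatal, leading to discontinuation, gastrointestinal) are all of TEAEs. All AEs and SAEs are also listed.

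**Protocol 7.6.3** takes a simpler line: reported AEs with onset "during treatment (i.e. treatment-emergent AEs) will be included in the analysis". It adds: "The numbers (frequency) and incidence rates of AEs and SAEs will be summarized during exposure to UX007 throughout the study". It sets no condition on earlier history of the same term.

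**Protocol 8.5.4.1** defines what a site must record: "All AEs (i.e. any new or worsening in severity or frequency of a preexisting condition". On timing: "All AEs will be collected from the time the subject signs informed consent through 30 days following the last dose of study drug". Related AEs that start later are also to be reported.

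**Records before the first CL202 dose.** Protocol 7.5.4.1: "Medical history will be obtained at the Baseline Visit for all subjects not previously enrolled in UX007G-CL201". Protocol 7.5.1: "The Baseline Visit may occur in conjunction with the last scheduled visit from study UX007G-CL201". SAP 8.5 uses CL201 history for Rollover subjects in the medical history tables. SAP 8.9.1 does not say which records decide whether a term was present before the first dose.

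**The concern.** The two limbs of the SAP rule do not meet. The first excludes any term present *prior to* the first dose. The second brings back only a term present *at* that dose, and only if its severity rises. A term that came and went before the first dose and returns on treatment satisfies neither. The second limb also names severity alone, although the protocol treats a rise in frequency as an adverse event.

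This matters more here than in a trial of untreated patients. SAP 3.1 states that every subject has already taken triheptanoin, so some will have had terms that resolved before entry. Protocol 6.1.1 makes related AEs and SAEs the primary endpoint, and the tables that report it are TEAE tables. Listings keep the omitted events but do not give incidence.

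The SAP is also inconsistent within itself. SAP 7.2.4 assigns a missing causality as definitely related for any AE starting on or after the first dose, whatever its history. A recurrence could therefore be imputed as definitely related and still be absent from the treatment-related TEAE table.

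**Working it through.** The documents give no event count or rate that depends on the definition, so there is no figure to reproduce. The check applies both rules to the same events.

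**Rules**
- SAP 8.9.1, literal: (event on or after first CL202 dose AND term not present before it) OR (term present at first dose AND severity increased).
- Protocol 7.6.3 read with 8.5.4.1: onset during treatment, where a worsening in severity or frequency is itself an AE.

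| # | Event | SAP 8.9.1 | Protocol |
|---|---|---|---|
| 1 | New term on treatment | counted | counted |
| 2 | Term resolved before first dose, recurs on treatment, same grade | not counted | counted |
| 3 | As 2, higher grade | not counted | counted |
| 4 | Ongoing at first dose, higher grade on treatment | counted | counted |
| 5 | Ongoing at first dose, same grade, more frequent on treatment | not counted | counted |
| 6 | New term 20 days after last dose | counted | not counted |
| 7 | New term 60 days after last dose, reported as related | counted | not counted |

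The rules differ in 5 of 7 cases: the SAP is narrower in 2, 3 and 5, and wider in 6 and 7. These are constructed cases, so 5 of 7 is not a rate. Row 5 needs both protocol sections, because 7.6.3 itself does not mention frequency. Rows 6 and 7 take treatment to end at the last dose, which 7.6.3 does not spell out.

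**How far back the rule looks decides rows 2 and 3**
- *Only CL202 AE pages.* These start at consent. Where consent, Baseline and first dose fall close together, almost no prior terms exist and the loss is near zero.
- *CL201 AE records as well.* Rollover subjects then carry a look-back through the feeder study (up to its Week 52 visit); Non-Rollover subjects have no counterpart in CL201.
- *Medical history.* CL202 collects it only from subjects not previously enrolled in CL201. For Rollover subjects it would have to come from CL201.

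Under the second or third option the same recurrence could count in one group and not in the other. SAP 8.1 generally analyses the two groups separately.

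**Scale per subject.** Planned enrolment is up to 40 (SAP 3.5). If a subject's only episode of a term is dropped, that term's incidence falls by 1/40 = 2.5 percentage points; two subjects give 2/40 = 5 points and four give 4/40 = 10 points. Within one group of n < 40 the step is 100/n, so larger. How many subjects would be affected is not in the documents.

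**The case against.** The best case for the SAP has five parts.

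1. *The SAP is only adding detail.* Protocol 7.6 calls its statistics a guide, and 7.6.3 leaves further safety detail to the SAP. That permits elaboration, but it does not explain a rule that excludes events the protocol includes.
2. *The recurrence gap needs a look-back that the SAP never prescribes.* SAP 8.9.1 keeps referring to the first dose in this study, and SAP 8.5 does not say that history is coded to preferred terms. This stands as a limit on size: if only CL202 pages are used, little is lost. It does not settle the rule, because classification by preferred term points away from an episode-level reading.
3. *Frequency worsening is covered elsewhere.* Seizure frequency, the obvious example, is analysed by diary and EEG under SAP 8.8. That is an efficacy analysis and does not place a worsening recorded as an AE, or as an SAE, in the safety tables.
4. *The missing end date is cautious.* Routine collection stops 30 days after the last dose, and admitting post-dose onsets errs toward inclusion. This stands, so the end date is a secondary clarification.
5. *The consequences are limited.* There is one arm and no safety testing, all AEs are listed, and SAP 4.1 words its endpoints as AEs and SAEs. But the incidence tables in 8.9.1 are of TEAEs, so the reported rates still follow the flag.

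**Conclusion.** The point holds as a conflict between definitions that can give a wrong count. It should be fixed before the tables are programmed. It rests on the literal, term-level reading of SAP 8.9.1 and on reading Protocol 7.6.3 together with 8.5.4.1.

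The size is not derivable, and neither is the net direction. Recurrences and frequency worsening are lost. Post-dose onsets, and missing start dates set to the first dose under SAP 7.2.3, can add events.

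A reader might infer three stronger claims that the documents do not support:
- *That incidence will be materially understated, or the groups made non-comparable.* Both depend on which earlier records feed the flag, which is not stated.
- *That about 6 of 40 subjects lose a gastrointestinal event*, from the 2 of 14 with early digestive symptoms in the open-label study in Protocol 5.2.3 (2/14 × 40 = 5.7). That would estimate subjects entering with a resolved term, not recurrences omitted, and no recurrence rate is given.
- *That the open end date distorts up to a quarter of the data.* For a subject stopping at Day 92, 30/(92 + 30) = 24.6% of collection time falls after the last dose; at Day 1104 it is 30/(1104 + 30) = 2.6%. These are shares of time, not of events.

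**What to change.** Replace the definition in SAP 8.9.1 with one that works on AE records rather than preferred terms:

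- A TEAE is any AE with onset on or after the first CL202 dose and up to 30 days after the last dose, which matches the collection window in Protocol 8.5.4.1.
- This includes a recurrence of a term that resolved before the first dose, and a worsening in severity or frequency recorded as an AE.
- An AE ongoing at the first dose also counts if it worsens afterwards.
- Onsets after the last dose are flagged within the tables, not removed. Ending the definition at the last dose would take serious or fatal events that start soon after stopping out of the main tables.
- Related AEs with onset beyond 30 days are listed.
- The records that establish *ongoing at first dose* are named, and the same sources are used for Rollover and Non-Rollover subjects.

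**Cost.** One SAP paragraph and reprogramming of the flag, with no new data where worsening is entered as its own record. Reported incidence may rise slightly, and some recurrences of background disease will be counted. One limit should be stated in the SAP. Protocol 8.5.4.1 says: "Details of the AE must include severity, relationship to study drug, duration, and outcome". Frequency is not among these, so where a site only updated the original record, a frequency worsening cannot be recovered.

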6.1 Study Endpoints

6.1.1 Primary Endpoint

The primary endpoint of the study is the frequency of AEs and SAEs assessed as related to study drug over the Treatment Extension Period.

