7.6 Statistical Methods and Determination of Sample Size

The completeness of the data affects the integrity and accuracy of the final study analysis. Therefore, every effort will be made to ensure complete, accurate and timely data collection, and to avoid missing data. The procedures for handling missing, unused, or spurious data, along with the detailed method for analyses will be presented in the Statistical Analysis Plan (SAP); in general, missing data will be treated as missing unless stated otherwise. The information below is intended as a guide to planned analyses.

The statistical analyses will be reported using summary tables, figures, and data listings. Statistical tests will be one-sided at the $\alpha=0.05$ significance level. All analyses and tabulations will be performed using SAS[®]. Continuous variables will be summarized with means, standard deviations, medians, minimums, and maximums. Categorical variables will be summarized by counts and by percentages of subjects in corresponding categories. For time-to-event data, the Kaplan-Meier estimates will be computed and plotted. Graphical data displays may also be used to summarize the data. All raw data obtained from the CRFs as well as any derived data will be included in data listings. For certain data collected over time, the Generalized Estimating Equation (GEE) may be used as the marginal model approach.

Tests of treatment effects will be conducted at a one-sided alpha level of 0.05 and/or one-sided 95% confidence interval where possible. Each secondary endpoint will be tested independently at one-sided alpha=0.05. No adjustments for multiple comparisons will be performed.

Specific details of primary and secondary endpoints as defined in Section 6.1, and associated analyses will be provided in the SAP.

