4.1 Safety Endpoints

- Subject incidence and severity of Adverse events (AEs) and serious adverse events (SAEs)
- Subject incidence of treatment related AEs, AEs leading to discontinuation, fatal AEs, and Gastrointestinal AEs using the standardized MedDRA query (SMQ) as listed in [Appendix C](#).
- Prior and concomitant medication
- Observed value of vital signs and weight during the study
- Observed value of clinical laboratory test results and percentage of subjects who experience abnormal clinical laboratory results (i.e. outside of reference ranges) and/or clinically significant abnormalities
- The number and percentage of subjects with suicidal ideation and behavior assessment as measured by the Columbia Suicide Severity Rating Scale (C-SSRS)
- Physical examination
- Pregnancy testing if applicable

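### Subject incidence is the only adverse-event measure the SAP names; the event numbers and incidence rates planned in Protocol 7.6.3 are missing, and related serious AEs are only listed

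*SAP*

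**What the plan says.** Protocol 6.1.1 states: "The primary endpoint of the study is the frequency of AEs and SAEs assessed as related to study drug over the Treatment Extension Period". Protocol 7.6 passes the detail on: "Specific details of primary and secondary endpoints as defined in Section 6.1, and associated analyses will be provided in the SAP".

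Protocol 7.6.3 then describes two outputs in separate sentences. One is subject-based: "the percentage of subjects who experienced at least 1 occurrence of the given event will be summarized by treatment group". The other is event-based and tied to exposure: "The numbers (frequency) and incidence rates of AEs and SAEs will be summarized during exposure to UX007 throughout the study".

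SAP 4.1 gives subject incidence, with severity, for AEs and SAEs. For the related events it gives "Subject incidence of treatment related AEs, AEs leading to discontinuation, fatal AEs" and a gastrointestinal grouping. SAP 8.9.1 specifies the main table: "Subject incidence of TEAEs will be tabulated by SOC and preferred term". It says that serious, treatment-related, grade 3/4, fatal and discontinuation TEAEs will be summarized, without naming a measure. Treatment-related SAEs are named only among the listings. Exposure duration is derived (SAP 5.4) and summarized on its own (SAP 8.7.1).

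**The concern.** The protocol leaves the definition and analysis of its primary endpoint to the SAP, and the SAP defines it more narrowly than the protocol describes it. An analyst who follows the SAP as written would report the primary endpoint as crude subject incidence.

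Crude incidence has two limits here. First, it depends on length of follow-up, which can differ between subjects: Protocol 7.4.4.1 plans 3 years but allows earlier ending, for example on withdrawal of consent or when the drug becomes commercially available in the subject's region. Second, it counts a subject once however often the event recurs, so it cannot show the burden of repeated events over a long extension.

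Related serious AEs are a separate gap. They are part of the primary endpoint, but the summaries cover serious TEAEs and related TEAEs as two separate categories. The overlap cannot be recovered from those two tables.

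**Working it through.** **Comparison of the texts.** There is no stated figure to reproduce: the study is not powered and safety is descriptive.

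| Item | Protocol | SAP |
|---|---|---|
| Percentage of subjects with the event | 7.6.3 | 4.1, 8.9.1 |
| Number of events | 7.6.3 | not named |
| Incidence rate during exposure | 7.6.3 (undefined) | not named |
| Related serious AEs | 6.1.1 (primary endpoint) | 8.9.1, listing only |

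Three other SAP sections do not fill the gap. SAP 8.1 sets number and percentage of subjects as the default for categorical data. SAP 7.2.4 refers to an incidence summary when it imputes missing causality. SAP 8.7.1 does not use exposure as a denominator. The only normalized rates in the SAP are for seizures.

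**Illustration of size.** The documents give no AE rate and no drop-out rate, so every rate and drop-out share below is an assumption. The number of subjects, 40, is the planned enrolment (SAP 3.5).

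With a constant rate r per person-year (PY) and a fraction w of subjects followed for t years, crude incidence = Σ w × (1 − exp(−r × t)). Example: r = 0.5, all followed 3 years, 1 − exp(−1.5) = 77.7%. If half stop at 1 year, 0.5 × 77.7% + 0.5 × 39.3% = 58.5%, a fall of 19.2 points at the same risk.

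| Follow-up | PY | r = 0.1 | r = 0.3 | r = 0.5 | r = 1.0 | Fall (points) |
|---|---|---|---|---|---|---|
| All 3 years | 120 | 25.9% | 59.3% | 77.7% | 95.0% | – |
| Quarter stop at 2 years | 110 | 24.0% | 55.8% | 74.1% | 92.9% | 1.9 to 3.6 |
| Half stop at 2 years | 100 | 22.0% | 52.2% | 70.4% | 90.7% | 3.9 to 7.2 |
| Quarter stop at 1 year | 100 | 21.8% | 51.0% | 68.1% | 87.1% | 4.1 to 9.6 |
| Half stop at 1 year | 80 | 17.7% | 42.6% | 58.5% | 79.1% | 8.2 to 19.2 |

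**Repeat events**, all followed 3 years:
- Expected events = 40 × 3r.
- Affected subjects if events are Poisson = 40 × (1 − exp(−3r)).
- Affected subjects if risk varies between subjects (negative binomial, assumed k = 1) = 40 × (1 − 1/(1 + 3r)).

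| r | Events | Subjects, Poisson (events per affected subject) | Subjects, negative binomial (events per affected subject) |
|---|---|---|---|
| 0.1 | 12 | 10.4 (1.2) | 9.2 (1.3) |
| 0.3 | 36 | 23.7 (1.5) | 18.9 (1.9) |
| 0.5 | 60 | 31.1 (1.9) | 24.0 (2.5) |
| 1.0 | 120 | 38.0 (3.2) | 30.0 (4.0) |

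**A case where the rate is the less stable measure.** Assume 2 events per PY for the first 3 months and 0.1 per PY after that. Cumulative events per subject are 0.5 + 0.075 = 0.575 at 1 year, 0.675 at 2 years and 0.775 at 3 years.
- All 3 years: crude incidence 53.9%; pooled rate 0.775/3 = 0.258 per PY.
- Quarter stop at 2 years: 52.7%; (10 × 0.675 + 30 × 0.775)/110 = 0.273 per PY.
- Half stop at 1 year: 48.8%; (20 × 0.575 + 20 × 0.775)/80 = 0.338 per PY.

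In the last scenario the rate moves by +30.6% in relative terms and crude incidence by −9.5%. Neither measure is sufficient alone.

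**The case against.** The best counter-argument is about interpretation. Protocol 7.6 presents its statistical section as guidance rather than fixed commitments, and 7.6.3 says the SAP will add safety detail. The same section uses the word frequency for counts of subjects with abnormal laboratory results, and it carries template wording, such as a reference to treatment groups in a single-arm study. If numbers and rates of AEs simply meant n and %, the SAP would supply them. The SAP's statement that certain TEAEs will be summarized does not exclude event counts. With about 40 subjects and full listings, a reader could count related serious events by hand, and nothing inferential depends on the result.

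Part of this stands. The incidence rate is defined in neither document, so a person-time reading is natural but not certain. The SAP under-specifies rather than forbids. The effect is descriptive, and everything could be derived later from collected data.

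It does not remove the concern. Subject percentages have their own sentence in Protocol 7.6.3, and the literal wording of the other sentence counts AEs and SAEs, not subjects. On that wording, event numbers are missing whichever way the rate is read. The gap for related serious AEs does not depend on either reading, and a listing is not a summary of a primary endpoint.

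**Conclusion.** The concern holds and should be fixed. The SAP names no event count and no exposure-based rate for AEs, although Protocol 7.6.3 plans event numbers and incidence rates, and it gives no summary of related serious AEs. Confidence is high that the SAP omits these measures; the exact meaning of the protocol's incidence rate is less certain.

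The size cannot be fixed from the documents. Under the assumed constant rates it ranges from a shift of about 2 points in crude incidence with modest early stopping to about 19 points with heavy early stopping. Repeat events that subject incidence does not show run from about 1.2 to 4.0 events per affected subject. No test or treatment comparison is affected; what suffers is the completeness of the primary endpoint's description.

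**What to change.** In SAP 8.9.1:
- Keep subject incidence. Add the number of events, total person-years (SAP 5.4 exposure summed over subjects and divided by 365.25) and events per person-year. Do this for all and serious TEAEs (Protocol 7.6.3) and for related and related serious TEAEs (Protocol 6.1.1).
- Show these for the Full Analysis Set overall and by Rollover and Non-Rollover group.
- Define incidence rate, and state how recurrent or worsening events under one preferred term are counted.
- In the rate, count only onsets from first to last dose. Protocol 7.6.3 refers to AEs with onset "during treatment (i.e. treatment-emergent AEs) will be included in the analysis", and SAP 5.4 exposure stops at the last dose. The SAP's TEAE definition states no end, and AEs are collected to 30 days after the last dose (Protocol 7.5.4.8). Later onsets stay in the listings. State the window for each column so that counts and percentages are not read as covering the same events when they do not.
- Add a summary table of related serious TEAEs beside the listing.

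Labelling the primary endpoint as such in SAP 4.1 would help but is optional.

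The cost is SAP wording, a few table columns and one extra table. Event dates are collected, and exposure duration is already derived and summarized.
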